Flare Study Protocol

PI: [name] [name]

Co-Investigators: [name], [name], and [name]

Research Staff: [name] BS, [name] BS, MS, [name] RN, CCRP

1. Purpose

Triamcinolone acetate (TA) and methylprednisolone acetate (MA) are standard of care (SOC) medications administered in shoulder injections depending upon Physician preference. The Physicians involved in the study have observed a difference in the rate of call backs following shoulder injection due to a reported increase in shoulder pain following the SOC injection. The purpose of this study is to compare the incidence of a flare reaction following administration of TA versus MA intra-articular glenohumeral and subacromial injections.

For the study, a flare reaction is defined as an increase of 2 or more from the baseline score on the visual analog score (VAS) in the first week following the shoulder injection.

2. Patient Enrollment

The study is a non-randomized, prospective, parallel-cohort study among subjects treated according to standard of care. Subjects will be approached for participation after electing to receive a corticosteroid injection in the glenohumeral joint or subacromial space as part of their SOC treatment plan. Three months was allotted for enrollment into the MA cohort followed by three months of enrollment into the TA cohort.

3. Inclusion Criteria

Any patient aged 18 to 95 who pursues a corticosteroid injection in the glenohumeral joint or subacromial space from one of three primary orthopedic Sports medicine or Shoulder specialists.

4. Exclusion Criteria

Patients will be excluded if they have received a corticosteroid injection in the previous three months.

5. Outcome Measures

The primary outcome measure is the incidence of a Flare reaction.

Secondary measures include VAS scores collected at the three-month time point. Another secondary measure is “treatment failure,” defined as a VAS score equal to or greater than a subject’s baseline VAS score. Subjects that proceed to another injection or surgery will also be defined as “treatment failures.”

6. Study Procedures

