The consent form will be utilized to explain the study design to prospective subjects in a private room. Adequate time will be allotted for questions and answers with the study team. The pre-injection VAS will be administered in clinic. VAS scores for the week following injection will be obtained through a “home diary” data collection tool labeled with a subject code. After completing the “home diary” tool, patients will mail the stamped, form to the study administrator. The three-, six-, and twelve-month VAS scores will be collected by phone interviews with research staff.

7. Statistical Analysis Plan

Data will be collected and summarized by research staff. Advanced statistical analysis will be performed, including risk ratios for flare reaction development by cohort as well as standard and adjusted regression models.

8. Risk to Subjects

Subjects may experience tiresome or troublesome feelings while completing VAS scores through the “home diary” or phone interviews with research staff. Loss of confidentiality is a potential risk disclosed to subjects.

9. Benefit to Subjects

There are no direct benefits to subjects outside of the possible benefits of the SOC procedures being studied. However, the findings from the study may contribute to generalizable knowledge as assist with decision making practices at Campbell Clinic.

10. Subject Discontinuation

Subjects will not be contacted for subsequent study procedures if the subject withdraws from the study or if they are determined to have “failed” treatment.

11. Adverse Events

No incidental adverse events are expected as all study procedures are currently SOC.

12. Data Handling, Collection, and Record Keeping

Baseline VAS scores will be collected in clinic prior to injection. “Home diaries” will be mailed by subjects to research personnel in a manner that protects study confidentiality. Three-month VAS scores will be obtained through phone interviews conducted by research personnel. All data will be combined into a secure, password-protected electronic data capture (EDC) tool.

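### Ending contact once a subject has failed loses later VAS scores because of the outcome, biasing VAS summaries in a direction the documents do not fix

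*Combined protocol and SAP*

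**What the plan says.** Section 10 sets the stopping rule: "Subjects will not be contacted for subsequent study procedures if the subject withdraws from the study or if they are determined to have" failed treatment.

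Section 5 gives two routes to failure. The first is "defined as a VAS score equal to or greater than" the subject's own baseline. The second is re-treatment: "Subjects that proceed to another injection or surgery will also be defined as" treatment failures. Neither route has a time point.

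On the VAS itself, Section 5 says: "Secondary measures include VAS scores collected at the three-month time point". Section 6 goes further: "The three-, six-, and twelve-month VAS scores will be collected by phone interviews with research staff". Section 12 describes only the earlier scores: "Baseline VAS scores will be collected in clinic prior to injection", the week-one diaries, and "Three-month VAS scores will be obtained through phone interviews conducted by research personnel". Six- and twelve-month VAS is therefore scheduled in Section 6, but is not listed as an outcome in Section 5 and not mentioned in Section 12.

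Section 7 plans risk ratios for flare "as well as standard and adjusted regression models". It names no model for VAS, no rule for missing scores, and no way for failed subjects to enter a VAS comparison.

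**The concern.** Under Section 10 a bad outcome, or re-treatment, is itself the reason that later scores are not collected. Three groups of scores are exposed:

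- **Six- and twelve-month VAS.** If VAS failure is judged at the three-month call, both are lost for every subject who failed then. Those still contacted have been selected for having improved.
- **Three-month VAS, a listed secondary measure.** It is lost for anyone the staff know to have had another injection or surgery before the call.
- **Three-month VAS in subjects who flared.** Because failure has no time point, a week-one diary score at or above baseline could be read as failure. A flare is a rise of 2 or more, so every flare would qualify, and the three-month score would be lost for exactly those subjects.

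At stake are the VAS summary in each cohort and the VAS difference between cohorts.

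**Working it through.** The documents give no sample size, SD, effect size or failure rate, so there is no planned figure to reproduce. All inputs below are assumptions, chosen to show how the bias behaves.

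**Set-up.** Within a cohort, the three-month change from baseline is normal with mean m and SD s. The six-month change has the same mean and SD, and correlation r with the three-month change. Failure is a three-month change of 0 or more, and failed subjects have no six-month score. Then:

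- P(fail) = 1 − Φ(−m/s)
- mean six-month change in those still contacted = m − r·s·λ, where λ = φ(−m/s)/Φ(−m/s)

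The term r·s·λ is the amount by which the cohort mean looks too favourable.

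**Equal SD and correlation (s = 2.5, r = 0.6; means −2 and −3, true difference 1.00).**

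- m = −2: P(fail) = 0.212, λ = 0.3676, shift = 0.6 × 2.5 × 0.3676 = 0.551, observed mean −2.551
- m = −3: P(fail) = 0.115, λ = 0.2194, shift = 0.6 × 2.5 × 0.2194 = 0.329, observed mean −3.329
- Observed difference = 3.329 − 2.551 = 0.778

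With s from 2 to 3 and r from 0.3 to 0.8, kept equal in the two cohorts, the result runs from 0.911 (s = 2, r = 0.3) to 0.665 (s = 3, r = 0.8). A separate simulation with means −1.5 and −2.5 and r from 0.3 to 0.7 gave 0.89 to 0.67.

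**Unequal SD or correlation.**

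- Both means −2, r = 0.6, SD 2 against 3: failure 16% against 25%; shifts 0.345 and 0.769. A true difference of 0 reads 0.769 − 0.345 = 0.42, in favour of the cohort with more failures.
- Means −2 (SD 2) and −3 (SD 2.9), r = 0.6: failure 15.9% against 15.0%; observed means −2.345 and −3.478. A true 1.00 reads 1.13.
- Means −2 (r = 0.4) and −3 (r = 0.8), SD 2.5 in both: failure 21% against 12%; observed means −2.368 and −3.439. A true 1.00 reads 1.07.

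**What a model can recover.** In simulation (2,000,000 per cohort, s = 2.5, r = 0.6), six-month change was regressed on three-month change among non-failures within each cohort, then predicted for everyone. The true, observed-only and model differences were 0.998, 0.776 and 0.998. With scores clipped to 0–10 and regression on baseline and three-month VAS, they were 0.844, 0.640 and 0.846. At 100 per cohort the model's standard error was 0.397, against 0.352 with all scores collected (0.397/0.352 = 1.13, about 13% larger).

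**What it cannot recover.** Suppose failed subjects really score d points off the line fitted in non-failures, for example after further treatment. In the equal-SD case the real difference is 1 + (0.212 − 0.115) × d, which is 0.81 at d = −2 and 1.19 at d = +2, while the model stays at 1.00. The observed-only shrinkage would vanish at d = −(1 − 0.778)/0.097 = −2.3. A subject with no three-month score has nothing recorded after week one from which to predict.

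**The case against.** The strongest case on the other side has four parts.

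- **The quantified harm falls on an unlisted measure.** Every figure above concerns six-month VAS, which Section 5 does not name. This stands, and it limits the weight of the point. Section 6 nevertheless commits staff to collecting those scores.
- **The loss of three-month VAS may be small.** It needs re-treatment before the call and staff knowledge of it, and no contact is scheduled between the diary and that call. This stands: the documents do not allow the group to be sized.
- **Treating failure as an end state is a coherent strategy.** Re-treated subjects are still counted as failures, and their later VAS partly measures the later treatment. This stands as an option, but the plan would have to state it as the way failure enters the VAS comparison, and it does not.
- **Section 7 allows adjusted regression, which can remove most of the bias.** This is true for three-month VAS failures if the right covariates are used and the fitted line holds for them. Section 7 specifies neither the covariates nor a rule for missing scores.

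A reader might infer that differing failure rates must shrink the cohort difference. The documents do not support that. It follows when the two cohorts share one SD and one correlation, and nothing in the plan says that they do. A reader might also infer that the main result is compromised. It is not: flare is read from the week-one diary.

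**Conclusion.** The point holds as a fault in a collection rule that is cheap to repair. Followed as written, Section 10 loses scheduled VAS because of the outcome, and Section 7 says nothing about handling the loss.

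A summary of only those still contacted makes each cohort look better than it is: by 0.55 and 0.33 points in the worked case. This assumes that three- and six-month changes are positively correlated and that failed subjects do not later score far better than the fitted line. The cohort difference is biased, but its direction cannot be stated from the documents. A true 1.00 may read about 0.67 to 0.91, or 1.07 to 1.13, and a true 0 may read 0.42, depending on assumed SDs and correlations.

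No size is claimed for the three-month VAS. The loss in subjects who flared arises only if week-one diary scores count as failure, which the plan leaves open. The primary flare outcome is unaffected, and failure status is known for those who fail.

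**What to change.** - **Section 10:** let only withdrawal end study phone contact, so that every scheduled VAS is collected whatever the failure status. This concerns study calls, not treatment.
- **Section 5:** state when failure is assessed and whether week-one diary scores count towards it. Record the date of any further injection or surgery.
- **Section 7:** report VAS in all contacted subjects beside the failure composite, and state how scores after re-treatment are treated. Use baseline and three-month VAS in the model for later scores that are still missing.
- **Sections 5, 6 and 12:** reconcile the schedules and state whether six- and twelve-month VAS are outcomes.

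The cost is wording changes, one extra recorded date, and some extra short calls by staff who already make them. The downside is that scores after re-treatment include the effect of that treatment. Such scores can be set aside in analysis, whereas scores never collected cannot be retrieved.
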